d. Treatment side effects. Published reports suggest that 50,000 IU per day of vitamin D (note that the proposed study dose is 50,000 IU per week) can increase vitamin D levels to more than 150 ng/dl and cause hypercalcemia (35). The current dose for this study is one capsule of 50,000 IU per week which equates to about 7000 IU per day. The dose at which the Vitamin D is being administered has minimal side effects, which may include gastrointestinal symptoms of constipation, stomach upset, and loss of appetite. Symptoms associated with vitamin D toxicity include bone pain, nausea, and vomiting (35, 120). We will be monitoring patient labs and for these symptoms at all study visits (baseline, 3, 6 months). Telephone interview (months 2, 4) will be used when patients are not seen for these assessments as with our pilot study (see procedures).

e. Safety. The vitamin D levels will be sent to the endocrinologist who will monitor the labs for the study, and inform the PI if the supplement needs to be stopped. This will be done when a study subject has either: (1) hypercalcemia or (2) vitamin D level of greater than 100 ng/ml with normal serum calcium or symptoms of vitamin D previously listed that may be indicative of possible toxicity (35). Patients will be requested to return for a serum level of vitamin D within one month (since the half life is approximately two weeks) of stopping therapy (120) and then again at the end of the study. The depression assessment will be reviewed with the psychiatrist prior to enrollment and subjects will be monitored for depression over the course of the study when they are seen (baseline, 3, 6 months) as well as when they are not seen (months 2, 4) by telephone. Subjects will be withdrawn if there is significant worsening of depression (see Human Subjects). These protocols were followed for the pilot study and no adverse effects occurred.

2. Sample.

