Freezerworks, the biospecimen tracking software used in the repository, will also automatically assign specimen numbers to incoming specimens. These numbers will identify all donated specimens. The list that links these codes with patients' identifying information will be kept separate from all research specimens and clinical data.

Information that may readily identify patients will never be shared with anyone.

d. Retention, Adherence, and Drop Outs. To enhance retention, participants will be scheduled for visits on a day that is convenient for them (oftentimes Saturdays). Free parking will be provided for visits. Honorarium for data collection points will be given in a stepped manner (\$25-baseline 1, \$25 baseline 2, \$30-three months, \$35-six months, \$40 optional qualitative interview after 6 month visit) with a personalized thank you note. We have published on these strategies (114). To enhance adherence to treatment we will have automated weekly reminders to take supplements (preferred method: phone, e-mail, or text). Retention in our pilot study was 92% using these techniques. To assess for treatment adherence, we are obtaining blood vitamin D levels and requesting that patients bring their bottle (to count for the number of unused pills, if any) at both 3 and 6 months. For persons who drop out, we will assess the reason for drop out and the extent to which they require further treatment with referral to their provider as stated in informed consent document (Human Subjects).

4. Measurements (Appendix). Variables, measures, and times are delineated below. In our pilot study, respondent burden was not an issue. Measurements are in the Appendix.

	Variables	Measures	Timing
Aim 1	Depression (Primary)	Center for Epidemiologic Studies (CES-D), Patient Health Questionnaire (PhQ-9) Diagnostic Interview Schedule (DIS) Suicidal Assessment Form (if applicable)	0, 3, 6 months (Phone CES-D @ months 2, 4, and 9mos) Baseline 0, 3, 6 months
	Self- Management (Secondary) Self-Efficacy Diabetes Distress Self-Care Behaviors	Diabetes Self-Efficacy Scale Problem Areas in Diabetes Diabetes Self-Care Inventory , Summary of Diabetes Self-Care Activities Appraisal of Diabetes Scale	0, 3, 6 months 0, 3, 6 0, 3, 6
	Blood Pressure (Exploratory)	Blood Pressure (mm HG)	0, 3 , 6 months
Aim 2 Exploratory	Inflammatory Biomarkers Vascular Markers	e.g., CRP, IL-6, TNF alpha e.g., VEG-F and clotting factors	0,3, 6 months

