These exclusion criteria will be assessed over the phone verified at the baseline enrollment visit. In addition at baseline enrollment, the participant's depression will be verified using the diagnostic interview schedule. If during that interview the patient screens positive for self-harm, they will be excluded from participation (see Protection Against Risks, B2).

All eligible subjects will be randomized into either the treatment group (vitamin D 50,000 IUs) or the comparison group (5000 IUs). They will be requested to make 4 study visits for data collection over a period of 6 months (baseline data, prescription pick up 10 days later, 3 month data collection and 6 month data collection). Women will also be called at months 2, 4 and 9 months (as noted under 3.c) to assess for any issues related to the study supplement as well as to assess for depressive symptoms.

(2) Sources of Data. We will obtain questionnaire and interview data from all study subjects at baseline, 2, 3, 6 and 9 months. Other data collected will consist of the following: a) a phlebotomy draw for blood specimens (one tube of 5 ml for Quest labs and one tube of 5 ml for immune markers) will be drawn from the participant at baseline, 3 and 6 months; and b) body measurements from the participant's physical exam (BP, height, weight) at baseline, 3 and 6 months; c) Body composition scan using dual-x-ray absorptiometry (DXA) scans at baseline, d) Urinary specimens (8 tablespoons) at study visits. All medical data will be obtained from the subject. Access to medical records is not being requested.

(3) Potential Risks. The potential risk to the research participants includes hematoma at the site of the venipuncture when the blood is drawn at baseline, 3 and 6 months. Blood will be drawn by the staff that has been trained to do this, so risk of bleeding and hematoma will be minimized.

DXA will be used to measure body composition (which includes bone, lean, and fat mass). Prior to DXA, female participants will undergo a pregnancy test. Pregnant women will be excluded from the study due to the radiation. The radiation exposure with a DXA scan is about 12microSieverts, which is significantly less than the radiation absorbed by a passenger on a roundtrip transcontinental flight (about 60 microSieverts). The scan will take approximately 10 minutes to perform.

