There is the potential that patients may become depressed over the course of the study. If patients demonstrate significant increases in the depression scores (i.e., an increase of 30% or more), either Drs. [name] or [name] will be consulted, and a determination will be made regarding contact with the primary care provider and a referral to a mental health care provider (HIPPA signed, see protection against risks). This will be done for those in treatment and control group at all points of contact (phone or face to face). If during the course of the study patients begin any medication for mood (e.g., depression or anxiety), this information will be recorded. If the patient begins therapy during the course of the study, the therapist will be contacted to ensure that the study does not conflict with the patient's current treatment protocol.

Hypercalcemia is a potential side effect of persons taking higher doses of vitamin D and this lab will be monitored to ensure that it is not present at time of enrollment and does not increase over the course of the study by the endocrinologist. Most recent evidence demonstrates that hypercalcemia may not be a significant side effect associated with vitamin D (49). Vitamin D levels will be measured at baseline to ensure that the level is less than 32 ng/ml. It will also be monitored over the course of the study to ensure that the levels do not increase or that there are symptoms of toxicity. Safety procedures are listed (see protection against risks).

To decrease the possibility of hypoglycemia from fasting, patients will be asked to make sure that they eat a protein before bedtime and bring their morning diabetes medications to take with the breakfast that is provided. For persons taking insulin, they will be informed that if they take insulin in the evening, to contact their health care provider about the dose that they should take when fasting for morning blood draws. They will also be informed to bring their morning medications to their data collection visits to take with their breakfast.

B. Adequacy of Protection Against Risks.

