If during this time the nurse identifies any patient as having suicidal ideation and being at moderate to high risk for self-harm that requires urgent evaluation and intervention, s/he will page Drs. [name] or [name]. The women will be evaluated by either Drs. [name], [name] or psychiatry resident, who will confirm the treatment plan with the psychiatry attending on service that day. If the patient has active suicidal ideation and is deemed to be in need of immediate psychiatric care, a member of the research team will escort the patient to the emergency room. She will be seen by the psychiatry resident on call and reported to the psychiatry attending to confirm a treatment plan. Drs. [name] or [name] will follow-up with the delineated treatment plan as this will be important for communication with the patient's health care provider as well as for the integrity of the study. These individuals will not be eligible for participation. At baseline enrollment, both the treatment and control will receive a list of resources for mental health services developed by the clinical psychologist (as with our previous study), and will not be prevented from getting help if needed. In our previous depression study this occurred infrequently (<3%) over the duration of the study (i.e., 1 woman started an antidepressant and 1 woman restarted therapy as she has seen a therapist in the past).

During the course of the study, [name], psychiatrist and co-investigator or [name], psychologist and co-investigator, will work with the research staff and consult as necessary. During any time where the nurse identifies any patient as being at moderate to high risk for self harm or with significant worsening of depression (a 30% increase in the CES-D), Drs. [name] or [name] will be contacted and procedures previously described followed. Subjects will be withdrawn if there is significant worsening of depression per Drs. [name] or [name] in consultation with their primary care provider. Similarly, for persons who drop out, we will assess the reason for drop out and the extent to which they require further treatment in consultation with [name] or [name] and their primary care provider. These protocols were followed for the pilot study and there were no adverse events.

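### Women withdrawn for worsening depression are not asked for later CES-D scores, so loss of the primary outcome depends on the outcome; the bias is small if withdrawal is rare, and its sign cannot be known in advance

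*Combined protocol and SAP*

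**What the plan says.** - **Withdrawal.** V.1.e (Safety) has "Subjects will be withdrawn if there is significant worsening of depression (see Human Subjects"). VI.B(2) (Protection Against Risks) repeats the rule and leaves the decision to the study psychiatrist or psychologist, in consultation with the primary care provider. The sentence before it there requires those clinicians to be contacted for any woman "with significant worsening of depression (a 30% increase in the CES-D").
- **Softer steps first.** Under VI.A(3) (Potential Risks), a 30% rise leads to consultation, after which "a determination will be made regarding contact with the primary care provider and a referral to a mental health care provider". If a woman starts therapy, "the therapist will be contacted to ensure that the study does not conflict with the" treatment she is receiving. New mood medication is recorded. Many such women evidently stay in the study.
- **After leaving.** V.3 (Retention, Adherence, and Drop Outs): "For persons who drop out, we will assess the reason for drop out and the extent to which they require further treatment". VI.B(2) says much the same. Neither asks for a CES-D.
- **Contrast.** When the supplement is stopped for toxicity, V.1.e asks the woman back within a month and again at the end of the study.
- **Data collection.** The V.4 table lists "Phone CES-D @ months 2, 4, and 9mos". VI.A(2) says "We will obtain questionnaire and interview data from all study subjects at baseline, 2, 3, 6 and 9 months", without saying whether a withdrawn woman is still a study subject. The month 9 call in V.3.c is timed from completion of the intervention.
- **Analysis.** V.5.b fits a mixed model at baseline, 3 and 6 months with compound symmetry (other structures if necessary), plus an intention-to-treat analysis. V.5.c adds a pattern-mixture analysis if data are judged not missing at random.

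**The concern.** The rule that removes a woman operates on the scale that measures the primary outcome. When the trigger is a month 2 or 4 phone call, the triggering score also lies outside the primary model, so the model cannot condition on it. If the high dose is better, more comparator women cross the threshold and go missing after a bad score.

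Two things can follow. If their course would have been unchanged, the model fills the gap too optimistically for the comparator and the difference shrinks. If withdrawal brings referral and treatment that lower later scores, the model misses that improvement and the difference is inflated. Only the uncollected scores can show which applies. The intention-to-treat and pattern-mixture provisions are general and do not supply them.

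**Working it through.** **The plan's own figures.** V.5.d takes a 14-point fall on vitamin D and 7 in an earlier control group, a difference of 7. With the pilot baseline SD, d = 7/7.6 = 0.92. The stated effect size of .46 is d/2. Power at 30 per group is Φ(7/(7.6 × √(2/30)) − 1.96) = Φ(1.61) = 0.946, against the stated 95%. Attrition: 150/0.85 = 177, against the stated 180. Both reproduce.

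**How many women.** The documents give no figure for withdrawal through worsening. The pilot lost 4 of 50 for all reasons (8%, exact 95% CI 2% to 19%). It reported no worsening, but it was single-arm on 50,000 IU and so is silent on the comparator dose. Planned attrition is 15%. Assuming that one quarter of women meeting the 30% rise are withdrawn, the simulation gives 0.8% to 6.4% of women, about 1 to 12 of 180.

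**Simulation inputs** (200,000 women per arm; months 0, 2, 3, 4, 6)
- From the pilot: baseline mean 26.83, SD 7.6, truncated at 16; SD 8.9 at month 3 and 8.3 at month 6.
- Comparator month 6 mean 21 (V.5.d gives 21.4 for the earlier control group).
- Assumed: comparator month 3 mean 22 or 24; SD 8.9 at month 2 and 8.7 at month 4, with means interpolated; high-dose mean lower by 3.5 or 7 at month 6 and by 80% of that at month 3; 3-month correlation 0.4, 0.6 or 0.75, decaying or constant. This makes 2 × 2 × 3 × 2 = 24 settings.
- Assumed: a woman first reaching 1.3 × baseline at month 2, 3 or 4 is withdrawn with probability 0.25 or 1, and scores after withdrawal are lowered by 0, 4 or 8 points.
- Truth: the month 6 difference with every score kept. Analysis: maximum likelihood on months 0, 3 and 6, compound symmetric.
- Standard error at 75 per arm: 8.3 × √(2/75) × √(1 − r²), where r is the baseline to month 6 correlation. As r runs from 0.16 to 0.75 this is 1.36 × 0.99 to 1.36 × 0.66, or 1.3 to 0.9 points.

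**Bias at month 6, in CES-D points** (toward or away from no effect)

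| Withdrawn after trigger | Course unchanged | Care worth 4 points | Care worth 8 points |
|---|---|---|---|
| One quarter | 0.01 to 0.13 toward | 0.03 toward to 0.12 away | 0.02 to 0.28 away |
| All (upper bound) | 0.09 to 0.65 toward | 0.19 toward to 0.40 away | 0.06 to 1.05 away |

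At one quarter, the largest values are 0.11, 0.10 and 0.22 of a standard error. At 4 points, 14 of 24 settings are away by more than 0.02 and 4 are toward. With all withdrawn the maximum is 0.85 of a standard error, but 16 of 24 settings then exceed the pilot's 8% all-cause loss and 8 exceed 15%.

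**Variations at one quarter**
- Unstructured covariance: 0.02 to 0.09 toward (unchanged); nil to 0.11 away (4 points); 0.03 to 0.27 away (8 points).
- Care reaching every woman who triggers, withdrawn or not: 0.04 toward to 0.08 away (4 points); 0.01 to 0.19 away (8 points).
- Month 2 and 4 phone scores added to the model: within 0.01 of the truth if the course is unchanged, but the effect is overstated by 0.03 to 0.16 (4 points) or 0.07 to 0.32 (8 points).

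**Equal arms** (12 settings): bias 0.03 or less, which is simulation error.

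**Second simulation.** With 60,000 women per arm, correlations 0.3 to 0.6, half or all triggers withdrawn and a difference of about 7, bias was 0.1 to 0.5 toward no effect (unchanged), 0.05 toward to 0.5 away (care worth 5), and 0.3 to 1.2 away (care worth 10). The largest was 0.76 of a standard error, and there was none under the null beyond 0.04. The pattern is the same.

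**The case against.** The strongest reply is that this argues from silence. Withdrawal is undefined, the sentence in V.1.e closes a paragraph partly about stopping the supplement, and VI.A(2) plans questionnaires for all subjects. The consent text and some attachments are not available for review and might settle it. This stands in part: the documents do not forbid later CES-D collection. But the same paragraph asks women stopped for toxicity to return and makes no such request after worsening, so reading the plan as not asking is fair.

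Second, the 30% figure prompts a call to the clinicians and is not itself a withdrawal criterion. VI.C has the monitoring board review women with a 30% rise, along with attrition and its reasons. Both points stand. They make automatic withdrawal implausible, so the one-quarter row is more relevant than the upper bound. Board review reveals the process but does not recover scores.

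Third, the referral steps in VI.A(3) apply to 30% risers whether or not withdrawn. The variation that reflects this gives smaller figures, at most 0.19 points away.

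Fourth, a month 3 trigger is seen by the model and a likelihood analysis can use it. That is true, but month 2 and 4 triggers are not seen, and an unstructured covariance removes little of the bias.

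Finally, scores lowered by later care might not be wanted if the target is the effect without such care. The plan names an intention-to-treat analysis, for which they are wanted.

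**Conclusion.** The concern holds, as a modest one. As written, the plan loses CES-D scores because of CES-D scores, and nothing in the analysis section recovers them. The bias is at most 0.28 points, or 0.22 of a standard error, provided that withdrawal is discretionary and reaches about a quarter of women who trigger. It would approach one standard error only if nearly every trigger led to withdrawal and later care were very effective. It is absent when the arms do not differ, so the type I error is not at issue.

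The withdrawal fraction, the correlations, the month 2 to 4 course and the effect of care are assumptions, not documented values. Entry at CES-D 12 to 15 on antidepressants was not simulated. The sign stays open because it depends on scores that the plan does not ask for.

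**What to change.** Leave the clinical decision as it is. Reword V.1.e and VI.B(2) so that significant worsening ends study supplement, not study participation. State that these women are asked for the month 3 and 6 CES-D, by phone if needed, unless the clinician advises against contact, and that they are analysed in their randomised arm. If three in four respond, the one-quarter bias falls to at most 0.03 points (course unchanged, or care worth 4 points) or 0.07 points (care worth 8).

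A sensitivity analysis adding the month 2 and 4 phone scores is optional. It does not replace follow-up, because it overstates the effect when later care works.

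The cost is protocol and consent wording plus one or two CES-D calls for about 1 to 12 women. Some will decline, and phone scores differ in mode from visit scores, although the trial already uses phone CES-D.

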Freezerworks, the biospecimen tracking software used in the repository, will also automatically assign specimen numbers to incoming specimens. These numbers will identify all donated specimens. The list that links these codes with patients' identifying information will be kept separate from all research specimens and clinical data.

Information that may readily identify patients will never be shared with anyone.

d. Retention, Adherence, and Drop Outs. To enhance retention, participants will be scheduled for visits on a day that is convenient for them (oftentimes Saturdays). Free parking will be provided for visits. Honorarium for data collection points will be given in a stepped manner (\$25-baseline 1, \$25 baseline 2, \$30-three months, \$35-six months, \$40 optional qualitative interview after 6 month visit) with a personalized thank you note. We have published on these strategies (114). To enhance adherence to treatment we will have automated weekly reminders to take supplements (preferred method: phone, e-mail, or text). Retention in our pilot study was 92% using these techniques. To assess for treatment adherence, we are obtaining blood vitamin D levels and requesting that patients bring their bottle (to count for the number of unused pills, if any) at both 3 and 6 months. For persons who drop out, we will assess the reason for drop out and the extent to which they require further treatment with referral to their provider as stated in informed consent document (Human Subjects).

4. Measurements (Appendix). Variables, measures, and times are delineated below. In our pilot study, respondent burden was not an issue. Measurements are in the Appendix.

	Variables	Measures	Timing
Aim 1	Depression (Primary)	Center for Epidemiologic Studies (CES-D), Patient Health Questionnaire (PhQ-9) Diagnostic Interview Schedule (DIS) Suicidal Assessment Form (if applicable)	0, 3, 6 months (Phone CES-D @ months 2, 4, and 9mos) Baseline 0, 3, 6 months
	Self- Management (Secondary) Self-Efficacy Diabetes Distress Self-Care Behaviors	Diabetes Self-Efficacy Scale Problem Areas in Diabetes Diabetes Self-Care Inventory , Summary of Diabetes Self-Care Activities Appraisal of Diabetes Scale	0, 3, 6 months 0, 3, 6 0, 3, 6
	Blood Pressure (Exploratory)	Blood Pressure (mm HG)	0, 3 , 6 months
Aim 2 Exploratory	Inflammatory Biomarkers Vascular Markers	e.g., CRP, IL-6, TNF alpha e.g., VEG-F and clotting factors	0,3, 6 months
Treatment	Vitamin D, CA, PTH Levels Cardiometabolic Profile (CMP)	Serum Vitamin D, CA, PTH Serum labs Pill counts	0, 3, 6 months Baseline 3, 6 months
Contributory Obesity	Bone, Lean and Fat Mass Body Mass Index	Body Composition Scan Height, Weight	0 months 0, 3, 6 months
Diabetes	Glycemic Control Diabetes History and Care	HBA1c, Fasting glucose Diabetes Care Profile	0, 3, 6 months 0, 3, 6 months
Lifestyle Factors	Physical Activity Dietary Intake Sun Exposure Depression History	Godin Leisure-Time Exercise NHS 4 –item Questionnaire Block Diet Inventory Sun Exposure Tool s Diagnostic Interview Schedule	0, 3, 6 months 0, 3, 6 months 0, 3, 6 months
Other Factors	Sleep Quality of Life Diabetes Symptoms Anxiety Stress	Pittsburg Sleep Quality Index Ferrans Quality of Life Index Diabetes Symptom Scale State Trait Anxiety Cohen Stressor Scale	0, 3, 6 months

Social support Sociodemographic Information	MOS Social Support Sociodemographic Form	
Family Demographics Family Resources Family Quality of Life	Questionnaire FIRM Global Family Quality of Life Scale	0 (baseline and visit 2), 3, 6 months, and time of the qualitative interview. After 6 month visit
Qualitative Interview	Interview Guide (Optional Consent)	
Urinary Microbiome Overactive Bladder Tool Pelvic Floor Distress Inventory	Clean Catch Urine Specimen Microbiome and Phage activity OAB-q PFDI ICIQ	0 (baseline and visit 2), 3 and 6 months
[name] Lab Protocol (Appendix 2) Physical Exam	History and Physical Exam (UTI history)	0, 6 months

a. Depression Outcomes. The CES-D and the Diagnostic Interview Schedule (DIS) will be used.

(1) The CES-D (20 items) is well accepted for depression screening. The Center for Epidemiologic Studies Depression Tool is 20 items and measures symptoms of depression and their severity (0=none to 3=most of the time). A cutoff score of ≥ 16 has been used to indicate depression. The tool has excellent internal reliability (Cronbach alpha from .85 to .90). It has also been reported that the CES-D and the Beck Depression Inventory performed comparably as depression screening tools (118, 121). In our SWEEP trial, the CES-D was reliable (Cronbach alpha from .87 to .92) and was validated by the DIS. We were able to detect changes in level of depression symptoms and whether patients changed from the depressed to the non-depressed category using the CES-D guidelines (59). The Patient Health Questionnaire 9 (PHQ-9) is used in clinical practice to assess for depression and will be used to compare to CES-D and DIS (Kroenke et al., 2001).

(2) The DIS will be used to screen and verify mental information. It is a structured mental health interview that uses the criteria specified in the Diagnostic and Statistical Manual of Mental Disorders (DSM-IV) to generate diagnoses that can be used for research purposes (125, 126). It has been reported that results of the DIS correlate significantly with clinical diagnoses (127-128). It will be used to obtain a history of mental illness, depression characteristics (e.g., suicidality, # of previous depressive episodes, age of onset, and duration of episodes) and to verify the CES-D measure. **(3) Suicidal Assessment form** was developed by [name] and will be used to assess for those patients who have positive ideation on the DIS and/or positive score on the PHQ-9 with item #9.

b. Self-Management Outcomes include Self-Efficacy, Diabetes Distress, and Self Care Behaviors.

(1) Diabetes Self-Efficacy Scale was developed by Lorig and based on previous chronic-disease self-efficacy scales (130). It consists of 8 items that assess an individual's confidence in caring for their diabetes on a likert scale from "1=not confident" to "10=totally confident". It has established reliability of .83 (131) and has been reported to be effective in capturing self-efficacy for persons in diabetes clinical trials (132, 133).

(2) Diabetes-Related Distress (PAIDS) is a 20-item tool that measures the current burden of diabetes and its treatment. A sample question includes the following: Feeling discouraged with your diabetes treatment plan? which is scored on a 5-point scale (0=not a problem to 4=serious problem). Higher scores indicate greater emotional distress. The PAIDS has high internal reliability (alpha= .95). Predictive as well as concurrent validity have been established by correlations with other measures (e.g., psychosocial factors, regimen adherence, and glycemic control) (134, 135). The responsiveness of the tool to detect changes in distress has also been established using data from seven prospective diabetes intervention studies (136).

(3) Self-Care Behaviors: (a) Self-Care Inventory was developed to assess patient's perceptions of the degree to which they adhere to treatment recommendations for diabetes self-care (1= never do it to 5= always do it). The tool has 16 items that addresses the areas of medication adherence, dietary regulation, exercise, and management of blood sugar (137, 138). The Self-Care Inventory unlike measures that only assess the frequency of self-care behaviors doesn't presume that all individuals have the same treatment prescription and thus is able to assess adherence to different treatment regimens (e.g., insulin or not taking insulin). Studies have used the tool which has demonstrated psychometrics of reliability (Cronbach alpha .87) and validity (correlations with diabetes distress, depression, and HBA1c) (137-139). (b) Summary of Diabetes Self-Care

Activities has 11 questions about self-care activities and 14 questions about recommended activities (Toobert et al. 2000) (c) Appraisal of Diabetes Scale (ADS) which is items to assess patient perceptions of diabetes (Carey et al., 1991). **c. Blood Pressure Outcome.** Blood pressure will be measured in a standardized fashion using calibrated equipment in accordance with JNC guidelines (140). The protocol and training developed for the ongoing international studies assessing blood pressure by [name], co-investigator will be used. Blood pressure will be measured using the Omron Automatic Digital Blood Pressure Monitor (model HEM-7471c, Omron Healthcare, Bannockburn, IL, USA). After at least 5 minutes of resting, with the antecubital fossa at heart level, 3 blood pressure readings will be taken 5 minutes apart and the mean of the last 2 used for analysis (141).

d. Inflammatory and Vascular Biomarkers. (1) C-Reactive Protein (high sensitivity) will be measured by either [name] team or Quest Lab depending upon price agreement. **(2) Cytokines (e.g., TNF- α , IL-6 IL-1)** will be measured by [name] and his team in their lab (see Resources) using the **radioimmunoassay or with the** technique of Randox Technologies, "Evidence InvestigatorTM". This compact Biochip array system is comprised of a super-cooled Charge Coupled Device (CCD) camera and unique image processing software. We have already validated this Biochip technology for blood samples in preliminary studies. The results of the Biochips are comparable to results obtained by individual ELISAs for each of the individual parameters. Several cytokines, chemokines and growth factors can be analyzed simultaneously. **(3) Vascular Factors (e.g., VEG-F)** will be measured by [name] using similar methodologies described above.

e. Treatment (1) Labs: Serum vitamin D, calcium and PTH will be measured for each time by **Quest Laboratories** which is accredited by the College of American Pathologists (CAP) and Clinical Laboratory Improvement Amendments (CLIA) and has performed these assays for our pilot study at minimal cost. Quest will send the results either electronically or by fax with the patient ID number, initials, and date of birth. There will be no other identifiers on the labs. **Serum vitamin D** will be measured by liquid chromatography/tandem mass spectrometry (LC-MS/MS) which is the standard for the measurement of vitamin D and its components. This method provides a total 25 hydroxyvitamin D (25 OH- D) which includes 25 (OH) D₂ and the 25 (OH) D₃. Thus, we will be able to determine the effectiveness of vitamin D₃ supplementation. **PTH Intact and calcium** will be measured by Quest. The PTH is measured via an immunoassay and Calcium is measured by spectrophotometry

Cardiometabolic Profile will be measured by Quest Laboratories to assess normal lab function prior to enrollment as recommended by the FDA. This test includes the assessment of: Albumin, Albumin/Globulin Ratio (calculated), Alkaline Phosphatase, ALT, AST, BUN/Creatinine Ratio (calculated), Calcium, Carbon Dioxide, Chloride, Creatinine with GFR Estimated, Globulin (calculated), Glucose, Potassium, Sodium, Total Bilirubin, Total Protein, Urea Nitrogen. **(2) Vitamin D Pill counts:** At 3 and 6 month visits, supplement bottle will be checked for number of unused pills and reason for not taking.

f. Contributory Factors include obesity, diabetes, and lifestyle factors.

(1) Obesity (a) Body composition (which includes bone, lean and fat mass) will be measured using dual-emission x-ray absorptiometry (DXA) with a whole body scanner (Discovery W by Hologic) provided by [name] (co-investigator) who has an international study on vitamin D. The protocol for that study will be used: (a) an intrinsic CV will be determined by the DXA machine by the scanning of a phantom and (b) all DXA operators will be required to complete an intra-observer CV. The method for assessing body composition using DXA has been reported to be precise, accessible, and requires short scanning (142-144). The percent body fat measured by DXA has been used in examining vitamin D and its relationship to weight in postmenopausal women (145-146). **(b) Body Mass Index** will be calculated from weight using an electronic calibrated scale and height using a stadiometer.

(2) Diabetes: (a) Glycemic Control will be measured by hemoglobin A1C using the DCA 2000 (Miles Diagnostic Division). The within CV is 2.1 to 4.5% and the between CV is 0.8 to 4.4%. Fasting blood sugar will also be measured by Quest Laboratory from the Cardiometabolic Profile previously listed. **(b) Diabetes History and Care** will be measured using the Diabetes Care Profile from the Michigan Diabetes Research and Training Center. This has information on demographics and medical information such as current treatment, comorbidities, all medications (e.g., diabetes, depression), and previous diabetes education. Development, validity, and reliability of the Diabetes Care Profile have been reported (147). Demographics related to family composition (e.g., children) will be measured as well.

(3) Lifestyle: (a) Physical Activity: Short physical activity scale called the Godin Leisure-Time exercise Questionnaire which is 2 questions and assesses level of activity and if it is regular enough to work up a sweat (<http://www.godin.fsi.ulaval.ca/Fichiers/Quest/Godin%20leisure-time.pdf>). In addition, 4 items from the Nurses Health Study that asks the number of minutes per week for recreational outdoor activities, indoor activities (e.g., standing, sitting), usual walking pace, and number of flights of stairs per day.

(b) Food Dietary Intake (which includes vitamin D and calcium will be assessed by the Block Questionnaire(s). These have been developed using a data-based approach from the National Health and Nutrition Examination Survey (N-HANES) to create the selection of the foods, appropriate portion sizes and nutrient composition selected. The questionnaire for this study has about 110 food items to estimate usual and customary intake of a wide array of nutrients and food groups. The food list and nutrient database for its analysis were developed from the Block 1998 Food Frequency Questionnaire. The food list was developed from (NHANES) 1998 to 2002 dietary recall data and the nutrient database was developed from the USDA Food and Nutrient Database for Dietary Studies. Food is quantified in terms of portion size and pictures are provided to enhance accuracy (151, 152). The 110 item will be administered at second baseline visit and 6 months and the shorter version which assesses vitamin D and calcium only will be measured at baseline to capture this information for all enrolled subjects.

(c) Sun Exposure: Participants will be enrolled in the fall or early spring as these are the times that we have identified depresses subjects in our previous studies. To assess for sun exposure two methods will be used: amount of sun exposure and seasonality. (1) Amount of sun exposure has been developed using a method develop by Barger-Lux and Heaney (153) where sun exposure is assessed by the amount of time in the sun and usual attire worn. A quantifiable sun exposure is generated. (2) Season of study enrollment will also be recorded as a measure of sun exposure as done by other studies (116). (3) Cancer Sun Exposure Tool which is 14 items to screen for sun exposure (Glanz et al., 2008).

(d) Other Factors: Factors that contribute to the overall health of persons with diabetes will also be assessed and include sleep using the validated Pittsburg Sleep Index (Buyssee et al., 1998), perceived quality of life using Ferrans Quality of Life Index (Ferrans, 2013), and diabetes symptoms developed by Grootenhuus (1994), and state-trait anxiety developed by Speilberger (1983), the Perceived Stressor Scale developed by Cohen (1983) and the MOS Social Support tool developed by Sherbourne and Stewart (1991). Addition of assessment for sarcopenia, muscle function, and falls has been added as Appendix 2 with scientific justification.

(e). Family Quality of Life Outcomes: (1) Family Inventory of Resources for Management (FIRM). Used to assess internal family and social support services. Reliability ($\alpha = 0.87-0.92$) has been strong in families with chronic illness ([name], Sawin & Brei, 2013; Sawin, Brei, Buran, & Fastenau 2003). (2) FQOL is the “overall appraisal of the domains of life important to the family” measured with a 3-item scale, The G-FQOL Scale (parent perception of their off-spring QOL, their own QOL and their FQOL) reported on a scale from 0 (poor) to 100 (excellent). The G-FQOL Scale has strong preliminary reliability ($\alpha = 0.86 - 0.90$) in a study of women of children with chronic condition ([name], Sawin, Brei & Schiffman, 2015). (3) Qualitative Interview Questions developed by [name] to assess how patients manage their health after the study and how the family may impact their ability to manage their health (i.e., diabetes and/or mood) will be conducted after the 6 month study visit. An optional consent to participate will be obtained. The consent indicates that the audiotape will be transcribed word for word into a written document (transcript). The audiotape and transcription will be destroyed when the study is complete.

(f) Urinary Microbiome and Self-Report Measures. (1) Assessment of the urinary microbiome will occur in the laboratory of [name] at LUMC. Three tests will be conducted on the urine: the (i) general screen of bacteria, (ii) 16S rDNA sequencing, and (iii) both EQUC and standard urine cultures. Each sample will be labeled with the participant’s identification number from the parent grant and refrigerated. Samples not used will be biobanked (repository consent approved). (2) Assessment of urinary symptoms will include the use of the use of the (a) Overactive Bladder Questionnaire (QAB-q) which has been used in women with diabetes

